## Study Overview

TSQM v II = Treatment Satisfaction Questionnaire for Medication Version II

MusiQoL = Multiple Sclerosis International Quality of Life Questionnaire

MS = Multiple Sclerosis

## 7. Sample Size

A sample size of 106 subjects will be required to have 85% power to detect at least an 8 point difference in mean TSQM scores between Baseline and Month 6 or Month 12 measurements, with the standard deviation (SD) of 27.5 and a two sided significance level of 5%. Assuming a 20% drop out rate, approximately 133 patients will be enrolled into the study in the Netherlands, Switzerland and Belgium.

## 8. Overview of Planned Analyses

This SAP describes final analysis of the study. No interim analyses are planned for this study.

## 9. Changes to the Planned Analyses in the Observational Study Protocol

The statistical methods as described in the protocol were adopted. There are no changes to the planned analyses.

## **10. Analysis Set**

### **Safety Analysis Set:**

Safety analysis set is defined as all the subjects who provided informed consent and who received at least one dose of study treatment.

All analyses will be performed on safety analysis set.

## **11. General Specifications for Statistical Analyses**

Statistical analysis will be performed using Statistical Analysis System (SAS) version 9.1.3 or higher.

Descriptive statistics such as

- Number of subjects (n), number of subjects with missing values (Missing),
- Mean, Standard Deviation (SD),
- Median, first quartile (Q1), third quartile (Q3),
- Minimum and Maximum

will be provided for all continuous variables.

Mean, median, Q1 and Q3 will have more than one decimal place than the raw data and SD will have 2 decimal places more than the raw data. The decimal place for minimum and maximum values will be same as the raw data.

The frequency (n) and percentage will be calculated for all categorical variables including missing observations and the percentages will be rounded off to one decimal place.

Shapiro-Wilk test / Kolmogorov-Smirnov test will be used for test for normality of the data. All statistical tests are of explorative nature and corresponding p-values will be presented purely descriptive. All p-values will be rounded to four decimal places; p-values less than 0.0001 will be presented as '< 0.0001'.

95% Confidence Interval (CI) will be provided wherever applicable.

Adverse events will be coded using the Medical Dictionary for Regulatory Activities (MedDRA) Version 19.1 terminology for System Organ Class (SOC) and Preferred Term (PT).

### **Handling of missing data**

Missing information will be captured for quantitative as well as qualitative variables by the category “Missing” in the summary statistics. If there are no missing values, this will be indicated by ‘0’. Unless otherwise specified missing data will not be replaced.

## **12. Trial Subjects**

### **12.1 Disposition of Subjects and Discontinuations**

A table with

- Number of subjects screened
- Number of screen failure subjects
- Number of subjects enrolled in the study
- Number of subjects in Safety Analysis Set
- Number of Safety Analysis Set subjects who completed the study.
- Number of Safety Analysis Set subjects who discontinued the study together with primary reason for discontinuation (Lost to follow-up, Adverse event/ Serious adverse event, Discontinuation of Rebif is desired or considered necessary by the Investigator and/or the subject, Occurrence of an exclusion criterion, Subject withdraws consent (Reasons for Withdraws consent), Discontinuation of Rebif for any other reason (Reason for discontinuation)).

will be presented. Percentages will be calculated.

## 12.2 Outliers

Listing will be provided for subjects with outliers (if data available). Extreme data that are not explainable from clinical point of view are considered as outliers. Subjects with such outliers will be identified before the database lock. These outlier data will not be included in the analysis.

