## 16. Endpoint Evaluation

### 16.1 Primary Endpoint Analyses

TSQM v II was designed as a general measure of treatment satisfaction with medication, suitable for use across a wide variety of medication types and illness conditions. Findings in the development of this questionnaire indicated that the three dimensions on which patients evaluate their medication are: effectiveness, adverse effects and convenience. There was an additional overall satisfaction rating, representing individual balanced judgment across these three specific treatment attributes, potentially most predictive of patient satisfaction and adherence.

TSQM v II dimensions scores will be derived according to TSQM v II Scale Scoring Algorithm mentioned below.

- Global Satisfaction

will be summarized for baseline, Month 6, and Month 12, and change from baseline at Months 6 and 12 using descriptive statistics from Safety Analysis set.

A paired two-sided t-test will be used to test the null hypothesis that there is no difference in the TSQM v II global satisfaction scores between Baseline and Month 6, Baseline and Month 12.

The corresponding 95% two-sided CI will be presented.

**Scale Scoring Algorithm:** TSQM Scale scores range from 0 to 100 and no computed score should be lower or higher than these limits.

- **Effectiveness:**  $([(\text{Item 1} + \text{Item 2}) - 2] \text{ divided by } (12) \times 100$
- **Side Effects:**  $([\text{Sum of Item 4 to Item 6}] - 3] \text{ divided by } 12) \times 100$
- If one item is missing:  $([(\text{Sum of the two completed items}) - 2] \text{ divided by } (8) \times 100$
- **Convenience:**  $([\text{Sum of Item 7 to Item 9}] - 3] \text{ divided by } 18) \times 100$
- If one item is missing:  $([(\text{Sum of the two completed items}) - 2] \text{ divided by } (12) \times 100$
- **Global Satisfaction:**  $([\text{Sum of Item 10 to Item 11}] - 2] \text{ divided by } 12) \times 100$

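### Section 12.2 leaves out clinically unexplained extreme values without requiring a confirmed error, and no analysis that keeps them is planned

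*SAP*

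**What the plan says.** SAP section 12.2 gives the whole rule. The definition is: "Extreme data that are not explainable from clinical point of view are considered as outliers". On timing: "Subjects with such outliers will be identified before the database lock". On handling: "These outlier data will not be included in the analysis". A listing of the affected subjects is also promised. The section gives no numeric threshold, no list of variables, no named decision-maker and no requirement that a value be shown to be wrong.

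Three other places determine what the rule does in practice:

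- Section 10 defines one analysis set: "All analyses will be performed on safety analysis set".
- Section 11, on missing data: "Unless otherwise specified missing data will not be replaced". A removed score therefore drops out of the paired comparison.
- Section 16.1 sets the primary analysis: "A paired two-sided t-test will be used to test the null hypothesis that there is no difference in the TSQM v II global satisfaction scores", comparing Baseline with Month 6 and with Month 12, with a 95% confidence interval.

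No sensitivity analysis, with or without outliers, appears in the SAP.

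**The concern.** The rule turns on two judgements: that a value is extreme, and that nobody can explain it clinically. Neither shows that the value is wrong. A patient may report very low or very high satisfaction for reasons the record does not contain, and the answer is still valid. The same holds for a MusiQoL score, a high relapse count or a large number of missed injections. The last two are skewed by nature, so their large values carry much of the information.

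Identification before lock is a useful discipline, but it does less here than in a blinded comparative trial. Section 6 describes an open-label, single-arm study. Everyone is on the same drug, and calling a value extreme means looking at it, so its direction is apparent. Nothing in the rule protects the choice from that knowledge.

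The primary estimate is a mean change with a t-based interval, and both depend directly on the tails. Deleting from one tail moves the mean. Deleting from both tails leaves the mean roughly in place but shrinks the SD and so the interval. Because only the result without the values is planned, a reader would have no estimate to compare it with.

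**Working it through.** **Inputs.** From SAP section 7: SD 27.5, target difference 8 points, 106 evaluable subjects, 85% power, two-sided 5%, 20% dropout, 133 enrolled. From section 16.1: "TSQM Scale scores range from 0 to 100 and no computed score should be lower or higher than these limits". Assumed, because the SAP does not give them: normally distributed changes, and the number and direction of deletions.

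**1. Reproduce the plan's figure, to settle what the SD refers to.** Reading 27.5 as the SD of the paired change:

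n = [27.5 × (1.960 + 1.036) / 8]² = 106.09

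This matches the stated 106, and 106 / 0.80 = 132.5, hence 133. The paired reading of the SD is therefore used below. The sample size itself is not in question.

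**2. Deletion from the lower tail only.** If the lowest fraction p of a normal distribution is removed, the mean rises by SD × φ(z_p) / (1 − p).

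- p = 1%: 27.5 × 0.02665 / 0.99 = 0.74 points, which is 0.74 / 8 = 9% of the target.
- p = 2%: 27.5 × 0.04842 / 0.98 = 1.36 points, which is 1.36 / 8 = 17% of the target.

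Deletion from the upper tail gives the same shifts downwards.

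**3. Deletion of 2% from each tail.** The mean is unchanged. The SD ratio is

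√[1 − 2 × 2.0537 × 0.04842 / 0.96] = √0.793 = 0.890

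so the SD falls to 27.5 × 0.890 = 24.5. The number of values also falls, to 96% of the original, which widens the interval slightly. The ratio of interval widths is

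0.890 / √0.96 = 0.909

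so the interval is about 9% too narrow.

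**4. Simulation check.** Paired t-intervals, n = 106, true change 8, SD 27.5, 40,000 runs:

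| Values deleted | Mean change | 95% CI half-width | Coverage |
|---|---|---|---|
| None | 8.0 | 5.28 | 95.1% |
| 1 lowest (0.9%) | 8.7 | 5.16 | 93.8% |
| 2 lowest (1.9%) | 9.3 | 5.08 | 91.4% |
| 2 in each tail | 8.0 | 4.86 | 92.9% |

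The last row gives a width ratio of 4.86 / 5.28 = 0.920, or 8% narrower. This agrees with step 3, since 2 of 106 is slightly under 2%.

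**5. Limit on a single value.** Scores lie between 0 and 100, so no change can be below −100. If one of 106 changes is −100 and the rest average 8, deleting it moves the mean by (8 + 100) / 106 = 1.0 point.

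**The case against.** The best defence is that section 12.2 is meant as a plausibility screen. A value must be both extreme and clinically unexplained, and a patient who becomes dissatisfied or stops injecting is usually explainable. On that reading few or no genuine answers would be removed. Query procedures may also sit in documents not shown. This may well be the intent, but the text does not limit exclusion to errors, and someone following it literally could drop a valid value.

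Second, the handling is not hidden. Affected subjects are listed, and section 11 requires n and the number missing in summaries of continuous variables. A reader could see who was affected. What is missing is an estimate with the values retained.

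Third, section 11 declares all tests exploratory and p-values descriptive. That weakens any complaint about significance. It does not remove bias from the mean change and its interval, which remain the main result. The 0 to 100 range limits how far one TSQM value can move the mean, as step 5 shows, but does not make the effect negligible.

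Some stronger readings go beyond the documents:

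- A reader might infer that a sizeable share of unfavourable values, say 5%, would be removed. The rule does not trim percentiles, and nothing suggests that fraction or a one-sided pattern.
- A reader might take the 11% fall in SD in step 3 as the fall in interval width. It is not, because fewer values remain.
- A reader might infer that those who flag outliers are known to see the outcome results. The SAP does not say who decides or what they see, only that the design supplies no blinding.

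**Conclusion.** The point holds as a defect in the rule: exclusion is not tied to confirmed errors or impossible values, and no analysis that keeps the values is planned. Followed as written, it can bias the mean change or make its interval too narrow.

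The documents do not show that this will happen, nor by how much. The illustrative sizes are about 0.7 to 1.4 points for one-sided deletion of 1% to 2%, and an interval about 9% too narrow for 2% deleted in each tail. They rest on normal changes, on 27.5 being the SD of the paired change, and on assumed numbers and directions of deletion. If no value is flagged, the effect is nil. Relapse counts and missed injections fall under the same rule, but the effect on them was not calculated.

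This should be changed before lock. The study is exploratory, but the rule bears on its main estimate and is cheap to correct.

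**What to change.** Replace the last sentence of section 12.2 with:

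> Only values confirmed as data errors by query, or outside the possible range of the variable, are corrected or set to missing before lock. All other values stay in the main analyses. If any are flagged as outliers, the primary analysis is repeated without them as a sensitivity analysis.

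The planned listing stays. The cost is the wording change and at most one extra table, with no new data. The downside is a somewhat larger SD, and so a wider interval, if genuine extremes exist.

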## 13. Demographics and Other Baseline Characteristics

### 13.1 Demographics

The quantitative variable

- Age (Years)

will be summarized by descriptive statistics from Safety Analysis Set.

Age (Years) = (Date of Informed Consent- Date of birth + 1) / 365.25

The qualitative variable

- Gender (Male/ Female)

will be summarized as number and percentage from Safety Analysis Set.

### 13.2 Medical History

#### **Medical History Unrelated to Study Condition:**

Listing will be provided for the Medical history unrelated to study condition.

#### **Multiple Sclerosis History:**

The quantitative variables

- Time since MS onset (first symptom) (years)
- Time since Second attack (first relapse) (years)
- Number of MS relapses within 24 months prior to written informed consent

will be summarized using descriptive statistics from Safety Analysis Set.

Time since MS onset (first symptom) (years) = (Date of Informed Consent– MS onset (first symptom) date + 1)/365.25.

Time since second attack (first relapse) (years) = (Date of Informed Consent– Second attack (first relapse) date + 1)/365.25.

The qualitative variables

- Degree of recovery from first attack (Complete / Partial / No or minimal recovery)

will be summarized as number and percentage from Safety Analysis Set.

### **Prior MS Therapy:**

The quantitative variable

- Duration of prior MS Therapy (years)

will be summarized using descriptive statistics from Safety Analysis Set.

Duration of prior MS Therapy (years) = (End date of prior MS Therapy – Start date of prior MS Therapy + 1)/365.25.

The qualitative variables

- Received prior MS Therapy (Yes / No)
- Prior MS Therapy details (XXXX/ XXXXX)
- Reason(s) for discontinuation of prior MS Therapy (Adverse event / Lack of efficacy / Other)

will be summarized as number and percentage from Safety Analysis Set.

### **Prior MS Medication Related AEs and Associated Concomitant medications:**

Listing will be provided for the Prior MS Medication Related AEs and Associated Concomitant medications.

### **13.3 Other baseline characteristics**

#### **Expanded Disability Status Scale (EDSS):**

The quantitative variable

- EDSS score

will be summarized using descriptive statistics from Safety Analysis Set.

The qualitative variable

- EDSS score (0.0 / 1.0 - 1.5 / 2.0 - 2.5 / 3.0 - 3.5 / 4.0 - 4.5 /  $\geq 5.0$ )

will be summarized as number and percentage from Safety Analysis Set.

### **14. Prior or Concomitant Medications/Procedures**

Listing will be provided for prior and concomitant medications from Safety Analysis Set. No coding of medication will be done.

### **15. Treatment Compliance and Exposure**

Adherence is one of the secondary endpoint and will be described in section 16.2.

#### **Exposure:**

The quantitative variables

- Duration of Rebif Therapy (years)
- Rebif start dose (mcg)

will be summarized using descriptive statistics for Safety Analysis Set.

Duration of Rebif Therapy (years) = (Date of Last Rebif dose administered – Rebif Therapy Start Date + 1)/365.25.

will be summarized as number and percentage from Safety Analysis Set.

Listing will be provided for Rebif therapy record.

## 16. Endpoint Evaluation

### 16.1 Primary Endpoint Analyses

TSQM v II was designed as a general measure of treatment satisfaction with medication, suitable for use across a wide variety of medication types and illness conditions. Findings in the development of this questionnaire indicated that the three dimensions on which patients evaluate their medication are: effectiveness, adverse effects and convenience. There was an additional overall satisfaction rating, representing individual balanced judgment across these three specific treatment attributes, potentially most predictive of patient satisfaction and adherence.

TSQM v II dimensions scores will be derived according to TSQM v II Scale Scoring Algorithm mentioned below.

- Global Satisfaction

will be summarized for baseline, Month 6, and Month 12, and change from baseline at Months 6 and 12 using descriptive statistics from Safety Analysis set.

A paired two-sided t-test will be used to test the null hypothesis that there is no difference in the TSQM v II global satisfaction scores between Baseline and Month 6, Baseline and Month 12.

The corresponding 95% two-sided CI will be presented.

**Scale Scoring Algorithm:** TSQM Scale scores range from 0 to 100 and no computed score should be lower or higher than these limits.

- **Effectiveness:**  $([(\text{Item 1} + \text{Item 2}) - 2] \text{ divided by } (12) \times 100$
- **Side Effects:**  $([\text{Sum of Item 4 to Item 6}] - 3] \text{ divided by } 12) \times 100$
- If one item is missing:  $([(\text{Sum of the two completed items}) - 2] \text{ divided by } (8) \times 100$
- **Convenience:**  $([\text{Sum of Item 7 to Item 9}] - 3] \text{ divided by } 18) \times 100$
- If one item is missing:  $([(\text{Sum of the two completed items}) - 2] \text{ divided by } (12) \times 100$
- **Global Satisfaction:**  $([\text{Sum of Item 10 to Item 11}] - 2] \text{ divided by } 12) \times 100$

## 16.2 Secondary Endpoint Analyses

### Annualized Relapse Rate (ARR):

The quantitative variables,

- Annualized Relapse Rate before study entry
- Number of relapses during the study
- Annualized Relapse Rate on study

will be summarized for prior MS Therapy categories and overall using descriptive statistics from Safety Analysis Set.

Annualized Relapse Rate before study entry = (No. of Relapses within 24 months prior to written informed consent / (30.4375\*24)) \* 365.25

Annualized Relapse Rate on study = (Sum of No. of Relapses at month 6 and month 12/ Time on Study) \* 365.25

where,

Time on Study (days) = (Date of Study Completion or Date of study discontinuation - Date of first Rebif administration +1)

95% Confidence Interval (CI) will also be provided for Annualized Relapse Rate before study entry and on study.

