	
for Medication Version II (TSQM v II), in relapsing remitting MS (RRMS) patients who have discontinued their initial oral or injectable MS treatment, and have initiated treatment with Rebif.
 
Secondary objectives
 
 
• To evaluate the change in annualized relapse rate (ARR) in patients changing from initial oral or injectable forms of treatment to Rebif
 
• To assess therapy adherence to Rebif
 
• To determine the change in quality of life with Multiple Sclerosis International Quality of Life Questionnaire (MusiQoL) between Baseline, Month 6 and Month 12
 
• To document the reasons for discontinuation of initial MS treatment
 
• To evaluate the potential correlations between the following measurements: TSQM v II, ARR, adherence, reasons for discontinuation, MusiQoL and TSQM v II subscales
 
• To assess the difference between TSQM v II subscales between Baseline, Month 6 and Month 12.
 

Variables and Study Endpoints
	
The variables that will be evaluated in this study include demographics, MS history, prior and current medication, pertinent medical history, treatment satisfaction score determined with TSQM v II, ARR, treatment adherence, quality of life determined with MusiQoL questionnaire, reasons for discontinuation of previous therapy and adverse events.
 
Primary Endpoint:
 
 
• Treatment satisfaction score determined with TSQM v II
 

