	
from Baseline to Month 6 and to Month 12.
 
Secondary Endpoints:
 
 
• ARR (after 12 months of Rebif treatment)
 
• Adherence (after 6 and 12 months of Rebif treatment)
 
• MusiQoL (compare Baseline with after 6 and 12 months of Rebif treatment)
 
• Reason/s for discontinuation of initial MS treatment (oral or injectable).
 
 
Additional Secondary Endpoints:
 
 
• Correlation between TSQM v II and ARR; TSQM v II and adherence; TSQM v II and reason for discontinuation
 
• Correlation between MusiQoL and ARR; MusiQoL and adherence; MusiQoL and reason for discontinuation
 
• Correlation between TSQM v II subscales and adherence
 
• Correlation between TSQM v II subscales and reasons for discontinuation
 
• Difference between TSQM v II subscales at Baseline and after 6 and 12 months of Rebif treatment
 
• ARR before study entry compared to ARR at study end
 
• Association between ARR and treatment adherence.
 

Study Design
	
This is a prospective, multicenter, open label, uncontrolled, non-interventional, single arm study to measure treatment satisfaction of RRMS patients on Rebif after discontinuing initial first-line treatment.
 
This study consists of three visits:
 
 
• Visit 1: Baseline
 

	
 
• Visit 2: Month 6
 
• Visit 3: Month 12
 
 
This study will enroll RRMS patients who have discontinued their oral or injectable first-line MS medication and have decided to initiate subcutaneous Interferon beta-1a (IFN <math>\beta</math> -1a) (Rebif) treatment before Baseline measurements. MusiQoL and TSQM v II will be measured at Baseline, Month 6 and Month 12. Relapses and adherence will be assessed at Month 6 and Month 12. Adherence to Rebif therapy will be collected electronically using RebiSmart 2.0.
 
Since this is a non-interventional study, there will not be any study required clinical interventions and laboratory assessments.

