
Study Population and Eligibility Criteria
	
RRMS patients who have discontinued their initial MS treatment and for whom MS treatment is required according to the decision of the HCP and patient.
 
Inclusion Criteria:
 
The patient can be included when the patient
 
 
• Is male or female, 18 to 65 years of age (both inclusive), at the time of informed consent
 
• Is diagnosed with RRMS according to McDonald criteria 2010
 
• Has discontinued treatment with dimethyl fumarate (Tecfidera), teriflunomide (Aubagio), glatiramer acetate (Copaxone®), intramuscular IFN<math>\beta</math>-1a (Avonex®), pegylated interferon (Plegridy®), subcutaneous IFN<math>\beta</math>-1b (Betaferon®) or fingolimod (Gilenya®) within 6 months prior to Visit 1
 

- Is currently treated with Rebif using RebiSmart 2.0, for a maximum of 6 months prior to Visit 1
- Has a score on the Expanded Disability Status Scale (EDSS) between 0 to 5.0 inclusive
- Is willing and able to give informed consent.

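### The 'before' ARR window can contain up to 6 months on Rebif, so the before/after ARR comparison does not match the objective, and the direction of the bias depends on an ambiguous start date

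*SAP*

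**What the plan says.** The secondary objective in SAP section 6 is "To evaluate the change in annualized relapse rate (ARR) in patients changing from initial oral or injectable forms of treatment to Rebif". The matching additional secondary endpoint is "ARR before study entry compared to ARR at study end".

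Section 16.2 defines the first of these two rates. It begins "Annualized Relapse Rate before study entry = (No. of Relapses within 24 months prior to written informed consent" and divides that count by 30.4375 × 24 days, times 365.25. No treatment date enters the formula. The on-study rate takes the relapses recorded at Months 6 and 12 over time on study, and time on study runs from the first Rebif administration. Both rates are tabulated by prior MS therapy and overall.

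The inclusion criteria in section 6 say that an eligible patient "Is currently treated with Rebif using RebiSmart 2.0, for a maximum of 6 months prior to Visit 1". The qualifying drug must have been stopped "within 6 months prior to Visit 1". The Schedule of Assessments puts informed consent at Visit 1.

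In section 13.2 the only pre-study relapse variable is a count: "Number of MS relapses within 24 months prior to written informed consent". Start and end dates of prior therapy are used in section 13.2 and the Rebif start date in section 15, but not in the pre-study ARR.

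**The concern.** The objective contrasts two treatment periods, but the 'before' window is anchored to consent. Every eligible patient is already on Rebif at that point, and some have been for months. A relapse in those months falls on the 'before' side although the patient was taking the drug that the 'after' side is meant to describe.

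The on-study rate adds to the problem. If its clock starts at the first Rebif dose ever, the lead-in months enter both denominators, while their relapses enter only the 'before' numerator. The plan does not say whether that dose is the first ever or the first after enrolment.

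At stake is the one result that addresses the ARR objective. The breakdown by prior therapy also invites a reader to take the 'before' column as the relapse rate on that drug, which it is not.

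**Working it through.** **Inputs from the SAP.** 'Before' window: 24 months ending at consent (16.2). Rebif lead-in L: 0 to 6 months (section 6). On-study observation: 12 months for a completer (section 6). On-study relapses: those reported at Months 6 and 12, each since the last visit (16.2, 16.3).

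**Assumed, not in the documents.** Rates of b = 0.60 per year before Rebif and r = 0.30 on Rebif, each constant, so the true difference is 0.30.

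1. *The plan's own formula.* 30.4375 × 24 = 730.5 days, and 365.25/730.5 = 0.5. Each relapse adds exactly 0.5 to the 'before' ARR for every patient, whatever the treatment at the time.

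2. *Share of the window on Rebif.* L/24: 3/24 = 12.5%; 6/24 = 25%.

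3. *Measured 'before' rate.* [(24 − L) × b + L × r]/24. For L = 3: (21 × 0.60 + 3 × 0.30)/24 = 0.5625. For L = 6: (18 × 0.60 + 6 × 0.30)/24 = 0.525.

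4. *Reading A: clock starts at the first dose after enrolment.* The on-study rate is r = 0.30, so the difference is (b − r)(1 − L/24), attenuated by L/24.

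5. *Reading B: clock starts at the first dose ever.* The numerator covers 12 months and the denominator 12 + L, so the on-study rate is r × 12/(12 + L). For L = 3: 0.30 × 12/15 = 0.24. For L = 6: 0.30 × 12/18 = 0.20.

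| L (months) | 'Before' ARR | On-study, A | Difference, A | On-study, B | Difference, B |
|---|---|---|---|---|---|
| 0 | 0.600 | 0.300 | 0.300 | 0.300 | 0.300 |
| 3 | 0.5625 | 0.300 | 0.2625 | 0.240 | 0.3225 |
| 6 | 0.525 | 0.300 | 0.225 | 0.200 | 0.325 |

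6. *How general is the direction?* Under A the difference always shrinks towards zero. Under B the error is r × L/(12 + L) − (b − r) × L/24. At L = 6 this is r/3 − (b − r)/4, which is positive when b < 7r/3, about 2.3 times the Rebif rate. With no true change (b = r = 0.30), reading B still shows 0.30 − 0.20 = 0.10 as a fall.

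7. *Check of the fix.* End the 'before' window at Rebif start and let the Rebif numerator and denominator cover the same interval. For L = 6 the rates are then 0.60 (over 18 months) and 0.30, and the difference is 0.30.

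**The case against.** The best defence is that section 16.2 computes what the endpoint names: a rate before study entry. Nothing in the SAP calls it the rate on prior therapy, and the grouping by prior therapy can be read as defining subgroups. That is fair as to the label. The conflict is with the objective, which the endpoint is there to serve.

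The stakes are also limited. ARR is secondary, no before/after ARR test is planned in 16.2, and section 11 makes all tests exploratory. This bears on priority. It does not make the rate describe what the objective asks for.

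Three stronger readings are tempting, and the documents do not support them:

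- *That the comparison cannot show the change at all.* A patient with 24 months on the initial drug who starts Rebif at Visit 1 has an essentially unmixed window. The 25% share is reached only at the eligibility limit.
- *That much of the window is untreated time.* The eligibility summary lists no minimum time on the initial drug, so this can happen. With 6 months on the initial drug and 6 on Rebif, 12 of 24 months are on neither. But the SAP gives no distribution of prior-therapy duration, so the share is unknown.
- *That the effect is simply diluted by 12.5% to 25%.* That holds only under reading A.

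Replacing the 'before' rate by an ARR restricted to time on the prior drug also meets a sound objection. Intervals may be very short: one relapse in 3 months gives a rate of 4.0, against 0.5 now. Lack of efficacy is a listed reason for stopping, so interval length would depend on outcome.

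**Conclusion.** The concern holds in this form: the 'before' ARR can contain up to 25% Rebif time, with relapses on Rebif scored as 'before', and so does not match the objective of change from initial treatment to Rebif. The window share follows from the SAP alone.

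The bias has no fixed direction. At the 6-month limit, with assumed rates of 0.60 and 0.30, a true difference of 0.30 shows as 0.225 (25% too small) or 0.325 (about 8% too large: 0.025/0.30), according to how the first Rebif dose is read. These figures rest on constant rates, a 12-month completer and the maximum lead-in. The effect over the whole sample depends on the lead-in distribution, which is not given.

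This should be corrected, but it does not touch the primary endpoint.

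**What to change.** In section 16.2:

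- End the 'before' window at Rebif start: relapses from 24 months before consent to the day before the first Rebif dose, divided by the days in that interval, × 365.25.
- Count relapses on or after Rebif start in the Rebif period, with numerator and denominator covering the same interval. State explicitly which Rebif dose starts that period.
- Keep the 24-month rate only as a baseline descriptor labelled *all treatments, including Rebif lead-in*. Do not present the by-prior-therapy column as the relapse rate on that drug.
- If an ARR restricted to time on the prior drug is wanted, make it supplementary and pool it as total relapses over total person-time.

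This needs pre-study relapse onset dates, which the SAP does not confirm: section 13.2 names only a count. If they are not held, relabel the rate, show Rebif lead-in and prior-therapy duration beside it, and state the limitation. That needs no new data.

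**Cost.** SAP wording and a changed derivation. The Rebif start date is already used in section 15. The 'before' interval becomes unequal between patients and somewhat shorter, 18 instead of 24 months at the limit. If every patient had the maximum lead-in and relapses were Poisson at an unchanged rate, the standard error would rise by √(24/18) = 1.155, about 15%. With shorter lead-ins the loss is smaller.
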